6.2.3. Sub-Group Analyses

The following subgroup analyses will be provided for the primary efficacy endpoints with ITT analysis set without retrieved dropout data:

- By sex (male and female)
- By age group (4-8 and 9-11 years)
- By race (white, black, and other)
- By region (US and non-US)
- By previous therapy (ICS and NCS)

The subgroup analyses will be summarized using descriptive statistics by each week/visit and by treatment.

6.3. Secondary Efficacy Endpoints and Analysis

Secondary efficacy endpoints are as follows:

- Change from baseline in the weekly average of daily trough morning (predose and pre-rescue bronchodilator) PEF over the 12-week treatment period
- Change from baseline in the weekly average of total daily (24-hour) use of albuterol/salbutamol inhalation aerosol (number of inhalations) over weeks 1 through 12
- Change from baseline in the weekly average of the total daily asthma symptom score (defined as the average of the daytime and nighttime scores) over weeks 1 through 12
- Change from baseline in asthma control (measured by C-ACT) score over the 12-week treatment period
- Time to first onset of effect defined as the first decrease from baseline in daily rescue medication use
- Proportion of patients who discontinued from IMP for asthma exacerbation during the 12-week treatment period.

The sequential order of the secondary endpoints for multiplicity will be described in Section [7.2](#).

6.3.1. Variable Definitions

6.3.1.1. Weekly Average of the Daily Trough Morning PEF

A handheld device will be provided to patients at the SV and used to determine the morning PEF throughout the course of the study.

Morning PEF will be determined in the morning, before administration of IMP or rescue medications. Daily PEF time will be compared with IMP dose time.

If a PEF measurement is performed after the IMP dose, a 10-minute window will be allowed and included in the analysis, otherwise the PEF measurement will be ignored.

The first day postrandomization consists of electronic patient diary entry on the morning of the day after the RV (TV1). For the purpose of the efficacy analyses of weekly average of daily morning PEF measurements, the values will be the averages based on the available data for that week. The averages will be calculated as the sum of morning PEF values divided by the number of nonmissing assessments. There will be no imputation applied to postrandomization assessments.

6.3.1.2. Weekly Average of Total Daily (24-Hour) Use of Albuterol/Salbutamol Inhalation Aerosol (Number of Inhalations)

Patients will record the number of inhalations of rescue medication (albuterol/salbutamol HFA MDI) each morning and evening in the electronic patient diary. An entry of zero inhalations indicates no rescue medication is needed.

To calculate the total daily use of albuterol/salbutamol inhalation aerosol (number of inhalations), the electronic patient diary entry on RV (TV1) is defined as the first day of analysis.

The weekly average of the total daily inhalations is the average based on the available data for that week. The average will be calculated as the sum of total daily inhalations over the 7 days for each analysis week divided by the number of nonmissing assessments.

6.3.1.3. Asthma Symptom Score

Asthma symptom scores will be recorded in the patient's electronic patient diary each morning and each evening before determining PEF and before administration of IMP or rescue medications.

Daytime Symptom Score (determined in the evening):

- 0=No symptoms during the day
- 1=Symptoms for 1 short period during the day
- 2=Symptoms for 2 or more short periods during the day
- 3=Symptoms for most of the day which did not affect my normal daily activities
- 4=Symptoms for most of the day which did affect my normal daily activities
- 5=Symptoms so severe that I could not go to work or perform normal daily activities

Nighttime Symptom Score (determined in the morning):

- 0=No Symptoms during the night
- 1=Symptoms causing me to wake once (or wake early)
- 2=Symptoms causing me to wake twice or more (including waking early)
- 3=Symptoms causing me to be awake for most of the night
- 4=Symptoms so severe that I did not sleep at all

To calculate total daily asthma symptom score, analysis days are defined in [Table 4](#). The total daily asthma symptom score is the average of the daytime and the nighttime scores. The total daily asthma symptom score will be considered missing if either the daytime or nighttime score is missing.

The weekly average will be calculated as the sum of total daily asthma symptom scores over the 7 days for each analysis week divided by the number of nonmissing assessments.

6.3.1.4. Childhood Asthma Control Test Score

The C-ACT is a simple, patient-completed tool used for the assessment of overall asthma control. The first 4 items of the test are completed by the patient, while the last 3 items are completed by the patient's parents/legal guardians/caregivers. The first 4 items are scored on a 3-point scale (0 to 3) and the last 3 items are scored on a 5-point scale (0 to 5), with summation of all items providing scores ranging from 0 to 27. In case of missing item score, the average value will be calculated for that particular item and treatment. For the first 4 items, a patient has to have a minimum of 2 items in order to replace the mean value and for the last 3 items, a minimum of 1 item is required to replace the mean value.

These scores span the continuum of poor control of asthma (score ≤ 5) to complete control of asthma (score ≥ 25), with a cutoff score of 19 indicating patients with poorly controlled asthma.

The C-ACT will be completed by the patient and the patient's parents/legal guardians/caregivers at the investigational center, before any other assessments are performed, at the RV (TV1), TV4,

TV5, and TV6/IMPDV. The same parent/legal guardian/caregiver should complete the assessments at each visit, if possible.

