5.9. Randomization and Blinding

This is a double-blind, parallel-group, placebo-controlled, randomized clinical study. Patients who meet all randomization criteria at the RV will be stratified by previous therapy (ICS or NCS) and randomly assigned into a 1:1:1:1 ratio to receive Fp MDPI 25 mcg, Fp MDPI 50 mcg, FS MDPI 50/12.5 mcg, or placebo MDPI, twice daily, for the entire treatment period.

Randomization will be assigned via IRT. Patients being treated with a combination of ICS/NCS will be stratified as an ICS patient. Approximately 206 patients will be randomized into each treatment group. After the run-in period, patients and parents/legal guardians/caregivers will remain blinded to randomized treatment assignment during the study. In addition, the investigator and the sponsor's clinical personnel involved in the study will be blinded to the IMP identity after the run-in period until the database is locked for analysis and the treatment assignment is revealed.

No effort will be made to maintain a balance among treatment groups within an investigational center.

Patients will be randomly assigned to treatment groups by means of a computer-generated randomization list. The specifications for randomization will be under the responsibility and oversight of Teva Global Statistics. The output of the randomization process will be a patient randomization list.

The sponsor's clinical personnel involved in the study will be blinded to the identity of the treatment until the database is locked for analysis and the treatment assignment revealed.

The following criteria must be fulfilled at the RV:

- a. The patient continues to be in general good health, meeting the entry criteria.
- n. The average of the 5 highest values for trough morning FEV₁ obtained at home (by handheld device) out of the last 7 days prior to RV is within 40% to 85% predicted for age, height, sex, and race ([Quanjer et al 2012](#)).
- o. The patient's C-ACT score at the RV is ≤ 19 .
- p. The patient has demonstrated at least a 15% response to a bronchodilator from baseline FEV₁ within 30 minutes after 2 to 4 inhalations of albuterol/salbutamol HFA MDI (90 mcg ex-actuator) or equivalent at SV or during the run-in period as measured by handheld device. Note: The RV may not be conducted on the same day as the response to bronchodilator testing.

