2.5.2. Final Analyses and Reporting

All analyses identified in this statistical analysis plan will be performed only after the last patient has completed the study as defined in the study protocol. The statistical analysis plan and any corresponding amendments will be approved before database lock, in accordance to SOP GBP_RD_702 (Statistical Analysis Plan). The randomization codes will not be unblinded until database lock.

Any exploratory analyses completed to support study analyses, which were not identified in this statistical analysis plan, will be documented and reported in the CSR.

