4.3. Handling Withdrawals and Missing Data

4.3.1. Missing Data Imputation for Efficacy Analysis

The primary analysis and sensitivity analyses for the primary endpoints include reference-base multiple imputations for missing data and tipping point approaches as detailed in Section 6 and [Appendix A](#).

For endpoints analyzed using the mixed model for repeated measures (MMRM), there will be no imputation for missing data.

For all other variables, only the observed data from the patients will be used in the statistical analyses (ie, there is no plan to estimate missing data).

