6.3.2.4. **Change from Baseline in Asthma Control (Measured by Childhood Asthma Control Test [C-ACT] Score Over the 12-week Treatment Period**

The change from baseline in C-ACT score over the 12-week treatment period will be analyzed using an MMRM with effects due to baseline C-ACT score, sex, age, (pooled) investigational center, previous therapy (ICS or NCS), week, treatment, and week-by-treatment interaction. No explicit structure will be assumed for the covariance among the repeated measures. However, if there is a convergence program with unstructured covariance, then a compound symmetry covariance structure will be assumed.

6.3.2.5. **Time to First Onset of Effect in Daily Rescue Medication Use**

The time to first onset of effect, defined as the number of days elapsed from the date of randomization to the first date of decrease from baseline in daily rescue medication use. Patients who first have a decrease of effect will be counted as an event in the analysis; otherwise, patients will be right-censored at the date of last IMPDV assessments.

The analysis of time to first onset of effect will be performed using a log-rank test to compare the survival curves. Time to first onset of effect will be displayed graphically with a Kaplan-Meier figure, and median time to first onset of effect and associated 95% CIs will be provided.

Example SAS code for this analysis:

```
proc lifetest data=toasm method=KM outsurv=yyy;
  where treat in ("A", "D");
  time aval*cnsr(0);
  strata treat;
  ods output CensoredSummary=count
             Quartiles=qrt
             productlimitestimates=k mest
             HomTests = pvals(where=(upcase(test) = "LOG-RANK"));
run;
where: aval is days from the date of first double-blind study IMP
to the date of event or censoring. CNSR is the censoring flag (0=no
event [censored]; 1=event [meet criteria]). The code is executed for
each pair of treatment comparisons of interest.
```

6.3.2.6. Proportion of Patients Discontinued From IMP for Asthma Exacerbation During the 12-week Treatment Period

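### Filling a missing C-ACT item with the treatment-arm mean understates the standard error for secondary endpoint [D] and conflicts with the SAP's no-imputation rule for MMRM endpoints

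*SAP*

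**What the plan says.** The C-ACT has four child items scored 0 to 3 and three caregiver items scored 0 to 5, "with summation of all items providing scores ranging from 0 to 27" (SAP 6.3.1.4). It is completed at the randomization visit, TV4, TV5 and TV6 or the IMP discontinuation visit.

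For a missing item, the same section says: "In case of missing item score, the average value will be calculated for that particular item and treatment". Two conditions follow. The first covers the child block: "For the first 4 items, a patient has to have a minimum of 2 items in order to replace the mean value". The second covers the caregiver block: "for the last 3 items, a minimum of 1 item is required to replace the mean value".

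SAP 6.3.2.4 then states: "The change from baseline in C-ACT score over the 12-week treatment period will be analyzed using an MMRM". It gives no multiple imputation or variance correction for filled items. SAP 4.3.1 states: "For endpoints analyzed using the mixed model for repeated measures (MMRM), there will be no imputation for missing data". Protocol 6.2.4 has no item-level rule; it only asks centre staff to check the forms for completeness. C-ACT is endpoint [D] in both secondary testing tables (SAP 7.2, Tables 8 and 9).

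**The concern.** The filled value is a constant shared by every patient in the arm who lacks that item. It carries nothing from the respondent's other answers, which count only towards the minimum. Constants shrink the spread of total scores within an arm, and the model counts them as real observations. Both effects make the reported standard error too small and the confidence interval for [D] too narrow.

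Two problems of wording come with it. Because no visit is named, the mean could be taken at one visit or across all of them, so two programmers could derive different scores. And the rule imputes values for an endpoint that 4.3.1 says receives no imputation.

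At stake are the error bars on one secondary endpoint and, because a pass at [D] allows [E] and [F] to be tested, the nominal level at that step.

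**Working it through.** **The plan's own figure.** 4 × 3 + 3 × 5 = 27, so the stated range of 0 to 27 reproduces. The minimum-answer rules let up to 2 child items and 2 caregiver items be filled: 4 of 7 items, worth 2 × 3 + 2 × 5 = 16 of 27 points (59%).

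**Formula.** Let a share m of items be missing completely at random. Let V be the sum of the item variances, C the sum of the between-item covariances and n the arm size. After arm-mean filling:

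- reported variance of the arm mean = [(1 − m)V + (1 − m)²C] / n
- true variance of the arm mean = [V/(1 − m) + C] / n

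The first is (1 − m)² times the second, so reported SE / true SE = 1 − m, whatever the correlation between items. A nominal two-sided 0.05 test then has a true level of 2 × [1 − Φ(1.96 × (1 − m))]. The arm's item mean is unchanged by the filling, so under this mechanism the estimate itself is not biased.

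**Simulation.** 4000 null trials per setting; two arms of 181 (the SAP 2.4 evaluable number); one visit; the SAP's minimum-answer rules applied; inter-item correlation 0.3, 0.5 and 0.7. Item means and SDs are assumed (child 1.5 and 0.8; caregiver 2.8 and 1.3, before rounding to the scale). The comparator replaces the missing item with the mean of the answered items in the same block. Simulated ranges run across the three correlations.

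| Items missing (assumed) | SE ratio 1 − m | True level, formula | SE ratio, arm mean | Type I error, arm mean | SE ratio, own block mean | Type I error, own block mean |
|---|---|---|---|---|---|---|
| 1% | 0.99 | 0.052 | 0.98-1.00 | 0.048-0.056 | 0.99-1.01 | 0.047-0.055 |
| 2% | 0.98 | 0.055 | not run | not run | not run | not run |
| 5% | 0.95 | 0.063 | 0.94-0.95 | 0.061-0.067 | 0.99-1.00 | 0.049-0.054 |
| 10% | 0.90 | 0.078 | 0.89-0.91 | 0.072-0.088 | 0.98-1.02 | 0.048-0.059 |
| 20% | 0.80 | 0.117 | 0.80-0.81 | 0.110-0.115 | 0.99-1.01 | 0.050-0.051 |

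A separate single-visit check gave arm-mean SE ratios of 0.98, 0.95 and 0.89 at 2%, 5% and 10% missing, with type I error 0.055, 0.060 and 0.084. With 4000 trials, the Monte Carlo error of a 0.05 rejection rate is √(0.05 × 0.95 / 4000) = 0.003, so the 1% row cannot be told apart from no effect by simulation; there the formula carries the argument.

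**Accuracy per child.** At 5% missing, the root mean squared error of an affected child's total is 1.19, 1.03 and 0.83 points with the own block mean, against 1.16, 1.19 and 1.21 with the arm mean, at correlations 0.3, 0.5 and 0.7.

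**Missingness tied to poor control.** A further single-visit check used 206 per arm, item correlation 0.5 and two caregiver items missing in affected patients.

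- Null case, 10% of patients affected (0.10 × 2/7 = 2.9% of items): model SE 0.481 against an empirical SD of 0.490, a ratio of 0.98. Type I error was 0.056, against 0.050 with own means.
- True effect present, about 9% affected: the difference was 1.36 with full data, 1.31 with arm means and 1.36 with own means. Rejection rates were 0.767 (arm) and 0.762 (own).

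**The case against.** The strongest reply is that the effect is probably very small. The questionnaire is completed at the centre and staff check it, so few items should be missing. C-ACT is fourth among the secondary endpoints, reached only after three significant primary comparisons and passes at [A] to [C]. SAP 7.2 itself says that the scheme does not control overall Type I error. All of this stands, and it limits the point to a minor correction. It does not change the direction of the error or the clash with 4.3.1. SAP 7.2 also still claims control for a given strength over the six secondary endpoints.

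One could read 4.3.1 as covering missing visits only, with item filling as part of scoring. That is a sensible intention, but the SAP does not say so.

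A reader might infer four stronger things that the documents do not support.

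- *That needing the treatment code is a defect.* SAP 2.5.2 says "The randomization codes will not be unblinded until database lock", and the analyses follow lock. The primary imputations in SAP 6.2.2.2 and Appendix A also use treatment.
- *That arms are pulled towards their own means.* Filling leaves the arm's item mean where it was; only individual patients move.
- *That the minimum-answer rule makes sense only for a within-patient mean.* A limit on how much of a score may be filled is reasonable for any method.
- *That the effect always favours the drug.* If items go missing more often when control is poor, the difference shrinks (1.31 against 1.36 above), which nearly offsets the smaller standard error.

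**Conclusion.** The point holds as a minor one. As written, the rule makes the standard error for endpoint [D] too small by roughly the share of items missing: about 1-2% if 1-2% are missing, about 5% at 5% and about 10% at 10%. These rates are assumptions; the completeness check makes the low end more plausible.

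The 1 − m result assumes items missing completely at random at a single visit. The planned MMRM of change from baseline at weeks 4, 8 and 12 was not simulated, so the figures are a guide to size and not exact values for that model. The unnamed visit and the conflict with 4.3.1 rest on the text alone and need settling whatever the missing-item rate.

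**What to change.** In SAP 6.3.1.4, replace a missing item with the mean of the items answered by the same respondent, in the same block, at the same visit. Keep the present minimums: at least 2 of 4 child items and at least 1 of 3 caregiver items. If either is not met, leave the total missing for the MMRM. In SAP 4.3.1, add that this item-level scoring rule is an exception for C-ACT.

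The cost is one sentence in each section, made before database lock. It has two drawbacks. When items are only weakly correlated (about 0.3), the filled score is slightly less accurate per child (1.19 against 1.16 points at 5% missing). And a single caregiver answer may set the whole 15-point caregiver block. In the simulated settings the change brought the SE ratio back to 0.98-1.02.

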6.3.1.5. Time to First Onset of Effect

Patients will record the number of inhalations of rescue medication (albuterol/salbutamol HFA MDI [90 mcg ex-actuator] or equivalent) each morning and evening in the electronic patient diary. Total daily use will be calculated after the RV. The time to first onset of effect is defined as the first decrease from the weekly average baseline in daily rescue medication use.

6.3.1.6. Proportion of Patients Discontinued From IMP for Asthma Exacerbation During the 12-week Treatment Period

Once the investigator confirms that a case of asthma exacerbation requiring a significant alternative treatment has occurred, the event will be entered into the CRF as an asthma exacerbation event. Such patients will be discontinued from IMP. The proportion of patients discontinued from IMP for asthma exacerbation during the 12-week treatment period will be assessed.

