- q. The patient has had no significant changes in asthma medications during run-in, excluding the albuterol/salbutamol HFA MDI (90 mcg ex-actuator) or equivalent used as rescue medication or run-in placebo MDPI as supplied per protocol.
- r. The patient has not had a URI or LRI during the run-in period. Patients who develop a URI or LRI during the run-in period may be discontinued from the study and allowed to rescreen 2 weeks after resolution of symptoms.
- s. The patient has had no asthma exacerbation during the run-in period, defined as any worsening of asthma requiring any significant treatment other than rescue albuterol/salbutamol HFA MDI (90 mcg ex-actuator) or equivalent or the patient's

- run-in MDPI. This includes requiring the use of systemic corticosteroids, inhaled corticosteroids or other medications used to control asthma or are prohibited medications ([Appendix H](#)), and/or ER/urgent care clinic visit or hospitalization. Note: A single dose of nebulized albuterol/salbutamol will not meet the criteria for an asthma exacerbation. Emergency room/urgent care clinic visits where the treatment is limited to a single dose of nebulized albuterol/salbutamol will not meet the criteria of an asthma exacerbation.
- t. The patient has no clinical visual evidence (on oropharyngeal examination) of oropharyngeal candidiasis.
 - u. The patient has not experienced an adverse event that would result in failure to continue to meet selection criteria.
 - v. The patient has not used any of the prohibited concomitant medications during the run-in period (see Section [5.7](#) and [Appendix H](#)).
 - w. The patient has complied with home lung function assessments and patient diary (built into the handheld device) entry on at least 5 of the last 7 days prior to RV, including the following:
 - completion of daytime and nighttime asthma symptom scores
 - completion of daytime and nighttime rescue medication (albuterol/salbutamol HFA MDI) use (whether used or not)
 - completion of the morning and evening lung function assessments (FEV₁ and PEF) by handheld device on 5 or more of the 7 days immediately preceding the RV
 - recording of morning and evening IMP use on 5 or more of the 7 days immediately preceding RV

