3. ANALYSIS SETS

3.1. Intent-to-Treat Analysis Set

The intent-to-treat (ITT) analysis set will include all randomized patients.

In the ITT analysis set, treatment will be assigned based on the treatment to which patients were randomized, regardless of which treatment they actually received.

The ITT analysis set will serve as the primary analysis set for the efficacy analyses.

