The baseline 1-hour percent predicted trough morning FEV₁ is defined as the predose percent predicted trough morning FEV₁ measurement at the RV (TV1) at the **investigational center**. If the predose FEV₁ measurement is missing or the value is implausible, the baseline weekly at home average percent predicted trough morning FEV₁ will be used. If both, the baseline pre-dose FEV₁ measurement and the baseline weekly average percent predicted trough morning FEV₁ are missing, the baseline trough morning FEV₁ will be replaced by the overall baseline 1-hour value.

Trough Evening PEF:

The baseline trough evening PEF is defined as the average of recorded (nonmissing) trough evening PEF assessments over the 7 days prior to randomization. The first day before randomization consists of the electronic patient diary entry on the evening before the RV (TV1). Five out of the last 7 days nonmissing values are required for a patient to be randomized and to calculate the baseline value. In case the minimum of 5 nonmissing values cannot be satisfied during the entire run-in period (14-30 days), the patient's evening PEF baseline value will include days beyond 7 days prior to the randomization. If a minimum of 5 nonmissing values cannot meet, missing baseline value will be replaced by the overall trough evening PEF value.

Total Daily (24-Hour) Use of Albuterol/Salbutamol Inhalation Aerosol (Number of Inhalations):

Throughout the study albuterol/salbutamol inhalation aerosol will be provided to patients to be used as needed for the relief of asthma symptoms. Patients will record intake (number of inhalations) of rescue medication each morning and evening in the electronic patient diary. An entry of zero inhalations for both morning and evening will indicate a rescue-free 24-hour period.

The baseline value is defined as the average number of inhalations over each 24-hour (day and night) period over the 7 days prior to the date of the first dose. Patients should withhold their rescue medication for at least 6 hours prior to the morning of the RV (TV1), and all other study visits. Five out of last 7 days nonmissing values are required for patient to be randomized. No missing data imputation rule will apply.

Percentage of Rescue-free Days (24-Hour Periods):

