6.3.2. Analysis Methods for Secondary Efficacy Variables

The analysis of the secondary efficacy variables will be performed on the ITT analysis set without retrieved dropout data.

6.3.2.1. Change from Baseline in the Weekly Average of Daily Trough Morning (Predose and Prerescue Bronchodilator) Peak Expiratory Flow (PEF) Over the 12-week Treatment Period

The analysis of change from baseline in the weekly average of daily morning (predose and pre-rescue bronchodilator) PEF over the 12-week treatment period will be performed using an MMRM with effects due to baseline weekly average of daily morning PEF, sex, age, (pooled) investigational center, previous therapy (ICS or NCS), week, treatment, and week-by-treatment interaction. No explicit structure will be assumed for the covariance among the repeated measures. However, if there is a convergence problem with unstructured covariance, then a compound symmetry covariance structure will be assumed.

6.3.2.2. Change from Baseline in the Weekly Average of Total Daily (24-hour) use of Albuterol/Salbutamol Inhalation Aerosol (Number of Inhalations) Over Weeks 1 Through 12

The change from baseline in the weekly average of total daily (24-hour) use of albuterol/salbutamol inhalation aerosol (number of inhalations) over weeks 1 through 12 will be analyzed using an MMRM with effects due to baseline value, sex, age, (pooled) investigational center, previous therapy (ICS or NCS), week, treatment, and week-by-treatment interaction. No explicit structure will be assumed for the covariance among the repeated measures. However, if there is a convergence problem with unstructured covariance, then a compound symmetry covariance structure will be assumed.

6.3.2.3. **Change from Baseline in the Weekly Average of the Total Daily Asthma Symptom Score (Defined as the Average of the Daytime and Nighttime Scores) Over Weeks 1 Through 12**

The change from baseline in the weekly average of the total daily asthma symptom scores over weeks 1 through 12 will be analyzed using an MMRM with effects due to baseline score, sex, age, (pooled) investigational center, previous therapy (ICS or NCS), week, treatment, and week-by-treatment interaction. No explicit structure will be assumed for the covariance among the repeated measures. However, if there is a convergence problem with unstructured covariance, then a compound symmetry covariance structure will be assumed.

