6.4.2.10. Time to Consistent Onset of Effect in Daily Rescue Medication Use

The time to consistent onset of effect is defined as the number of days elapsed from the date of randomization to the first date of 3 consecutive days with a decrease from baseline in daily rescue medication use. Patients who have 3 consecutive days with a decrease in effect will be counted as an event in the analysis, otherwise, patients will be right-censored at the date of last IMPDV assessments.

The analysis of time to consistent onset of effect will be performed using a log-rank test to compare the survival curves. Time to first onset of effect will be graphically displayed with a Kaplan-Meier figure and the median time to first onset and associated 95% CIs will be provided.

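### Time to first onset of effect keeps children with zero baseline rescue use at risk although they cannot have the event, which lowers the power of secondary endpoint [E]

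*SAP*

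**What the plan says.** - **Event.** SAP 6.3.1.5: "The time to first onset of effect is defined as the first decrease from the weekly average baseline in daily rescue medication use".
- **Baseline.** SAP 4.2: "The baseline value is defined as the average number of inhalations over each 24-hour (day and night) period", taken over the 7 days before the first dose. It can be 0. The same section defines a baseline percentage of rescue-free days, so zero-use days are expected.
- **Entry.** Protocol 5.9 asks for diary entries on at least 5 of the last 7 days, including "completion of daytime and nighttime rescue medication (albuterol/salbutamol HFA MDI) use (whether used or not"). It sets no minimum rescue use.
- **Analysis set.** SAP 6.3.2: "The analysis of the secondary efficacy variables will be performed on the ITT analysis set without retrieved dropout data". SAP 3.1: "The intent-to-treat (ITT) analysis set will include all randomized patients".
- **Patients without the event.** SAP 6.3.2.5: "otherwise, patients will be right-censored at the date of last IMPDV assessments".
- **Test.** The comparison "will be performed using a log-rank test to compare the survival curves". The example code selects on treatment only.
- **Related endpoint.** SAP 6.4.2.10 repeats the construction for three consecutive days: "The analysis of time to consistent onset of effect will be performed using a log-rank test to" compare the curves, with the same censoring.
- **Testing order.** In Tables 8 and 9 (SAP 7.2), [E] stands directly before [F] in every column.

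**The concern.** A daily count cannot fall below 0, so a patient whose baseline average is 0 can never have the event. Nothing in either document excludes, stratifies or otherwise handles such patients. They stay at risk to the end in both arms.

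If only events were lost, the cost would be modest. The larger cost comes from the shape of the curves. One day below a 7-day average is an easy event, so patients who can have it mostly do so within days on either treatment. Both curves then flatten at the zero-baseline share. The faster arm runs out of susceptible patients first, its risk set fills with patients who cannot respond, and the later part of the log-rank sum cancels the early difference.

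At stake is a formal secondary endpoint. Under SAP 7.2 a p-value above 0.05 for [E] stops [F] in that column and stops the [E] comparisons to its right.

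**Working it through.** **The plan's own figures.** The documents state no power, event count or effect size for [E]. The only sample-size figures concern the primary endpoints. With n = 2(1.96 + 0.842)² SD²/d² per group, SD 22 and d 6.5 give 180, and SD 17 and d 5 give 182, against the stated 181. Then 181/0.88 = 206 randomized. So 206 per arm (412 per comparison), 84 days and 12% dropout come from SAP 2.1, 2.2 and 2.4. The zero-baseline share, the event rate and the drug effect on rescue use are assumptions.

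**Step 1: loss of events alone.** Schoenfeld: power = Φ(√(D/4)·ln HR − 1.96). With HR 1.4 (ln = 0.3365):
- no zeros, D = 412: Φ(10.15 × 0.3365 − 1.96) = Φ(1.46) = 93%
- 30% zeros, D = 288: Φ(8.49 × 0.3365 − 1.96) = Φ(0.90) = 82%

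**Step 2: why keeping them at risk costs more.** Take 10% zeros, a daily event probability of 0.3 on placebo, and HR 1.4, so the active probability is 1 − 0.7^1.4 = 0.393. Per 100 patients, 90 can have the event.
- Day 1 hazard in the full risk set: active 0.393 × 0.9 = 0.354, placebo 0.3 × 0.9 = 0.270. Ratio 1.31.
- After 5 days the susceptible patients left are 90 × 0.7^5 = 15.1 on placebo and 90 × 0.7^7 = 7.4 on active (because 5 × 1.4 = 7). Day 6 hazard: active 0.393 × 7.4/17.4 = 0.167, placebo 0.3 × 15.1/25.1 = 0.180. Ratio 0.93.

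The hazard ratio has reversed within a week, although the drug works equally well throughout in everyone who can respond.

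**Step 3: simulated log-rank, constant hazard ratio** (206 per arm, 84 daily steps, 12% dropout, 4000 runs per cell).

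| Daily placebo probability, HR | Zero share | As planned | Baseline >0 only |
|---|---|---|---|
| 0.3, 1.4 | 0% | 92% | 92% |
| 0.3, 1.4 | 5% | 58% | 91% |
| 0.3, 1.4 | 10% | 39% | 89% |
| 0.3, 1.4 | 30% | 12% | 79% |
| 0.03, 1.4 | 10% | 59% | 88% |
| 0.008, 1.5 | 10% | 76% | 80% |
| 0.008, 1.5 | 30% | 56% | 71% |

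With no drug effect, the planned test rejects in 5.2% of runs at 30% zeros and 5.8% at 50%, so its size holds approximately.

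**Step 4: simulated daily use.** Patient rates are gamma (shape 2, mean m), daily counts are Poisson, baseline is the 7-day average, and the drug reduces use by 30%. The implied zero share is (1 + 7m/2)⁻²: 4.5⁻² = 4.9% at m = 1 and 8⁻² = 1.6% at m = 2. A further 10% of never-users at m = 1 gives 0.1 + 0.9 × 0.049 = 14%. Without drug effect about half of patients have the event on day 1.

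| Onset of the 30% effect | Zero share | As planned | Baseline >0 only |
|---|---|---|---|
| Full from day 1, m = 1 | 5% | about 42% | about 84% |
| Full from day 1, m = 1, plus 10% never-users | 14% | about 19% | about 83% |
| Linear over 7 days, m = 1 to 2 | 2% to 14% | about 5-15% | about 10-21% |

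**Step 5: three-day onset (SAP 6.4.2.10), full effect from day 1.** Power is 67% as planned against 99% at 14% zeros (m = 1), and 93% against 100% at 11% zeros (m = 2).

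**The case against.** **The zero share may be small.** Children must have C-ACT of 19 or below and FEV₁ of 40-85% predicted (Protocol 5.9), after a 14- to 30-day placebo run-in without controllers (Protocol 3.1). That makes zero use less likely but does not exclude it. With slow events the loss is also small: 76% against 80% in the table. This stands, and the size must be stated as conditional.

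**The large power figures need an immediate effect.** About half of patients have the event on day 1, so a drug that takes a week to act has little chance to separate the curves in either analysis. Protocol 9.5.4.1 speaks of FEV₁ improving as early as 1 week on an inhaled corticosteroid and says nothing about rescue use. With a 14-day ramp both analyses reject in only 3-8% of runs. With an immediate effect but strongly autocorrelated daily use (correlation 0.7), the restricted test reaches only 29-40%. A reader might infer that removing zero-baseline patients restores 80% power or more in general. It does not: under gradual onset the main weakness is the one-day event itself. A fast effect is more plausible for the salmeterol combination (Table 9) than for fluticasone alone (Table 8).

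**The gating matters less than it looks.** [E] is reached only after all three primary tests and the earlier secondary tests in its column succeed. SAP 7.2 says this scheme does not control the overall type I error and that p-values are nominal. That also stands. A chance imbalance in zero-baseline patients would shift the Kaplan-Meier plateau, but it is ordinary sampling variation covered by the size of the test.

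**Restricting the set departs from ITT.** Protocol 9.5.4.3 requires the ITT set for all secondary endpoints. Stratifying meets this objection.

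**Conclusion.** The structural point follows from the text: patients with a baseline average of 0 are in the risk set, are censored, and cannot have the event. This lowers the power of [E] and blurs its Kaplan-Meier curves, without inflating type I error. If the effect is immediate, the loss is large even at modest zero shares: about 42% against 84% at 5%, and 19% against 83% at 14%. If the effect builds over 7 days, both analyses are weak (about 5-15% against 10-21%).

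A reader might infer that [E] is bound to fail, or that a false positive could result. The documents support neither. They do not give the zero-baseline share or the speed of onset, and the size of the test is kept. The point is a low-cost improvement in power and interpretability, not an error that undermines the trial's conclusions.

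**What to change.** Before unblinding, state in SAP 6.3.2.5 that the log-rank test is stratified by baseline average rescue use (0 versus above 0). The zero stratum contains no events and adds nothing to the observed, expected or variance terms, so the statistic equals that from patients with baseline above 0, while the ITT set is kept. Baseline use is fixed before randomization, so the comparison stays randomized.

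Show the Kaplan-Meier curves and medians for patients with baseline above 0, and report the number with zero baseline by arm. Apply the same to SAP 6.4.2.10, where the loss is smaller.

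The cost is a sentence or two in the SAP and one change in the example code; no new data are needed. The curves and medians will then describe only patients who could improve. The change does not cure the low sensitivity of a one-day event under gradual onset, and the report should say so when it interprets a non-significant [E].
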